## 6.2 Definition of Dose-Limiting Toxicity (DLT)

DLT will be defined as any of the events listed in this section that are at least possibly related to the investigational agent and that occur during the dose-finding period regardless of expectedness.

- Any INCB007839-related adverse event during the first course of therapy that leads to a dose reduction or results in the permanent cessation of therapy will be considered dose limiting. All dose modifications in all courses are to follow the guidelines provided.
- Any INCB007839-related adverse event during the first course of therapy that results in a delay of treatment > 7 days.

6.2.1 Non-hematologic dose limiting toxicity is defined as:

- Any Grade 4 non-hematologic toxicity
- Any Grade 3 non-hematologic toxicity with the exception of:
  - Grade 3 nausea and vomiting of < 5 days and responsive to anti-emetic treatment
  - Grade 3 elevation of transaminases that returns to levels meeting eligibility criteria within 7 days of study drug interruption and does not recur upon restarting drug.
  - Grade 3 fever or infection of fewer than 5 days in duration
  - Grade 3 hypophosphatemia, hypokalemia, hypocalcemia, or hypomagnesemia responsive to oral supplementation
- Any Grade 2 non-hematologic toxicity that persists for > 7 days and is considered medically significant or sufficiently intolerable by the patient that the toxicity requires treatment interruption
- Any deep venous thrombotic event (superficial phlebitis is excluded unless Grade 3 or 4 as above)
  - If a patient on this study has a thrombotic/thromboembolic event that is not related to the central line, treatment with INCB007839 will be discontinued and not restarted. Determination of attribution will be reviewed by the study team and discussed with PBTC Toxicity Committee and CTEP; and such events will be reported to the CTEP-AERS, PBTC DSMB, and the FDA as events of special interest in an expedited fashion. See special reporting requirements in [Section 10.3](#). In this event, enrollment will be halted until fully reviewed. In addition, any patient experiencing a non-central line-related thromboembolic event should have the

studies listed below performed as soon as possible after the event.

- Patients with a venous thrombosis should have the following assessed as soon as possible after thrombosis is suspected/confirmed:
  - CBC
  - Antithrombin
  - Protein C
  - Protein S
  - Factor V Leiden
  - Prothrombin G20210A gene analysis
  - Fasting serum homocysteine
  - Lupus anticoagulant assays
  - Anticardiolipin level
- Patients with an arterial thrombosis should have:
  - CBC
  - Fasting serum homocysteine
  - Lupus anticoagulant
  - Anticardiolipin level
  - LDL, HDL, triglycerides

#### 6.2.2 Hematologic dose limiting toxicity is defined as:

- Any Grade 4 hematologic toxicity with the exception of lymphopenia
- Grade 3 neutropenia with fever
- Requiring a platelet transfusion (threshold for transfusion is a platelet count of  $< 50,000/\mu\text{L}$ ) on 2 separate days (following adequate initial platelet transfusion to  $> 100,000/\mu\text{L}$ ) during a single course.

Management and dose modifications associated with the above adverse events are outlined in [Section 7](#).

#### 6.2.3 Dose-finding period

The dose-finding period begins with the initial dose of INCB007839 and ends on the last day of Course 1. Should there be a delay starting the subsequent course, dose-finding will complete on the start date of Course 2.

Management and dose modifications for toxicities which occur outside of the dose-finding period should also follow guidelines in [Section 7](#), however, these will not be considered dose limiting for the purpose of dose finding.

#### 6.2.4 Dose De-escalation

Dose de-escalation will proceed as follows:

- Course 1 will be started with an initial cohort of six (6) patients at  $120 \text{ mg/m}^2/\text{dose BID}$  (the dose levels to be tested are listed in [Table 3](#)). If more than 1 DLT is observed in 6 patients treated at Dose Level 1, de-escalation to Dose Level 0 will occur as outlined in

[Section 9.1](#). Only DLTs observed during the dose finding period of therapy will be used to guide dose de-escalation. Patients treated at Dose Level 0 who have a DLT will discontinue study therapy.

- If thrombosis occurs outside of the DLT period, this will be discussed with study team to determine attribution to study drug, potential dose-association, as well as consideration of the risk/benefit ratio of prophylaxis in subsequent patients.
- Patients enrolled on Dose Level 1 who have a dose-modifying toxicity outside of the dose-finding period (e.g., in Courses 2 and onward) should have the dose of INCB007839 reduced on subsequent courses to Dose Level 0. Patients can begin the subsequent course at the lower dose when the toxicity has resolved to Grade 1 or baseline and laboratory parameters are met as defined in [Section 3.1.9](#) and [3.1.14](#). Patients enrolled on Dose Level 0 who require a dose reduction will not receive further treatment on study and will be considered off treatment (see [Section 6.4.2](#)).

## 6.3 General Concomitant Medication and Supportive Care Guidelines

### 6.3.1 Steroids

Corticosteroids should be used at the lowest dose to control symptoms of edema and mass effect, and discontinued, if possible. Use of corticosteroids should be recorded in the RAVE database. Steroids should not be used to control other symptoms, e.g., nausea.

### 6.3.2 Anticonvulsants

Anticonvulsants should be used, if indicated. Use of anticonvulsants should be recorded in the RAVE database.

### 6.3.3 Growth Factors

Routine use of growth factors (e.g., G-CSF, GM-CSF, and erythropoietin) is not permitted. However, therapeutic use of G-CSF or GM-CSF in patients with serious neutropenic conditions, such as sepsis, may be considered at the investigator's discretion. Use of growth factors should be recorded in the RAVE database.

### 6.3.4 Anti-emetics

The use of anti-emetics will be at the investigator's discretion. Use of anti-emetics should be recorded in the RAVE database.

### 6.3.5 Febrile neutropenia

Febrile neutropenia should be managed according to the local institutional guidelines. Measures include laboratory testing, blood and urine cultures, and institution of broad-spectrum antibiotics.

### 6.3.6 Antihypertensive Medications

Hypertension should be managed, if indicated. Antihypertensives to maintain blood pressure below the 95th percentile for age, height, and gender (based on the normal blood pressure chart available in the Generic Forms section of the PBTC member's website) are allowed per the discretion of the treating physician according to institutional guidelines. Use of an antihypertensive

medications should be recorded in the RAVE database.

#### 6.3.7 Pneumocystis jiroveci pneumonia (PJP) prophylaxis

The use of medication (i.e., Bactrim) for PJP prophylaxis in patients on chronic steroids is recommended, but it is at the investigator's discretion.

#### 6.3.8 Neurosurgical or other surgical procedures

If a neurosurgical procedure or other surgical procedure is required for a reason other than tumor progression (e.g., the onset of hydrocephalus), these procedures should be documented but will not constitute criteria for declaring the patient "off therapy". INCB007839 should be held after any surgical intervention (with the exception of minor dental or dermatological procedures) for at least 28 days after surgery. LMWH should be held as indicated for the surgical procedure but restarted as soon as deemed safe by the treating surgeon.

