### 3.1.6 Prior Therapy

- Patients must have failed at least 1 standard, tumor-directed treatment besides surgery and recovered from the acute treatment-related toxicities (defined as  $<$  Grade 1) of all prior chemotherapy, immunotherapy, or radiotherapy prior to enrollment on this study.
- Patients must be  $\geq 28$  days from any prior surgery at the time of study enrollment (with the exception of minor dental and dermatological procedures).

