### 6.1 Agent Administration

This is a phase 1 dose finding trial in pediatric patients with recurrent/progressive high-grade glioma, including DIPG and other diffuse high-grade gliomas.

Given that the adult RP2D was 200 mg PO BID, we plan to evaluate the safety and tolerability of approximate pediatric equivalent dose based on a typical adult size of  $1.67 \text{ m}^2$ . Thus, we propose to start at  $120 \text{ mg/m}^2$  and de-escalate to  $80 \text{ mg/m}^2$  if this dose is not tolerable.

INCB007839 is administered orally (PO), twice a day each day for 28-day cycles. A medication diary will be required to ensure appropriate drug administration ([Appendix C](#)). The patient will be requested to maintain the medication diary documenting each dose of medication. The medication diary will be returned to clinic staff at the end of each course.

Given the known risk of thrombosis associated with INCB007839, DVT prophylaxis is required with low molecular weight heparin (LMWH, e.g., enoxaparin at 1 mg/kg/day [can be divided BID] with a maximum dose of 40 mg/day), with a goal of anti Xa level of 0.3–0.5 units/mL. DVT prophylaxis should continue throughout the duration of treatment and for 2 weeks after cessation of study drug, except as noted below.

- If a contraindication to DVT prophylaxis occurs (e.g., a new injury at risk of bleeding, planned invasive procedures, allergy to pork products, etc.), the study drug should be held at the time of LMWH cessation. LMWH should be held in these instances per institutional standards or the treating physician's discretion if no guidelines exist. If the temporary risk of anti-coagulation resolves, patients may restart INCB007839 with concurrent LMWH at the discretion of the treating physician.

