#### 6.1.2 Criteria to start subsequent courses

A course may be repeated every 28 days if the patient has at least stable disease and has again met laboratory parameters as defined in [Section 3.1.9](#), and [3.1.14](#) if applicable.

- If a patient does not meet these parameters at the end of the dose-finding period, then

INCB007839 should be held until parameters meet the criteria. If parameters are not met within 7 days of the scheduled course to begin, this is a dose-limiting toxicity (see [Section 6.2](#)) and dose reduction is indicated.

- If a patient does not meet these parameters at the end of subsequent courses (i.e., Course 2 and onward), then INCB007839 should be held until parameters meet the criteria. If parameters are not met within 7 days of the scheduled course to begin, this will require a dose modification (see [Section 7.0](#)).
- If INCB007839 is held for any reason other than toxicity (e.g., planned procedure), it can be restarted (with concurrent anti-coagulation) at the same dose and with counting of course days continuing (e.g., if INCB007839 is held on Days 13–16 of a course due to a shunt revision, restart INCB007839 and LMWH on Day 17 and continue counting course days for a 28-day course).

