### 7.1.2 Dose Modification for Non-thromboembolic Toxicity

A patient who has a non-thromboembolic toxicity at 120 mg/m^2 or is delayed > 7 days from the planned start of the next course should be dose reduced to 80 mg/m^2 on subsequent cycles. A patient who has a non-thromboembolic toxicity at 80 mg/m^2 or is delayed > 7 days from the planned start the next course will not receive further treatment on study and will be considered off treatment (see [Section 6.4.2](#)).

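### The shunt-revision example in Section 6.1.2 restarts study drug on Day 17, but Section 6.3.8 requires a hold of at least 28 days after surgery

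*Combined protocol and SAP*

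**What the plan says.** Section 6.3.8 covers neurosurgical and other procedures needed for reasons other than tumour progression, and gives hydrocephalus as its example. It says that "INCB007839 should be held after any surgical intervention (with the exception of minor dental or dermatological procedures) for at least 28 days after surgery". The exemption in parentheses is the only one. It also says that "these procedures should be documented but will not constitute criteria for declaring the patient" off therapy.

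Section 6.1.2 gives a general rule for holds: "If INCB007839 is held for any reason other than toxicity (e.g., planned procedure), it can be restarted (with concurrent anti-coagulation) at the same dose", with course days still counted. It illustrates the rule with this case: "if INCB007839 is held on Days 13–16 of a course due to a shunt revision, restart INCB007839 and LMWH on Day 17".

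Three other places bear on the point:

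- Section 6.1 deals with contraindications to low molecular weight heparin (LMWH), listing "a new injury at risk of bleeding, planned invasive procedures, allergy to pork products, etc". Study drug stops when LMWH stops, and then: "If the temporary risk of anti-coagulation resolves, patients may restart INCB007839 with concurrent LMWH at the discretion of the treating physician".
- Section 12.1 sets the dose count for evaluability in the dose-finding period: at least 45 of 53 doses, or 23 of 27 for Dose Level 0 patients on the morning dose only. Patients below 85% for reasons other than toxicity are replaced.
- Section 3.1.6 requires the same 28-day interval between surgery and enrolment, with the same dental and dermatological exception.

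**The concern.** A shunt revision falls within Section 6.3.8. The section is about neurosurgical and other surgical procedures, it names hydrocephalus, and it exempts only minor dental and dermatological work. Yet shunt revision is the case that Section 6.1.2 uses to show a four-day hold. A site facing one would find it named there and could restart on Day 17. Another site, reading Section 6.3.8, would wait at least four weeks. Each could cite the protocol.

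The event is foreseeable: Section 5.2.2.2 provides for cerebrospinal fluid sampling when a shunt is revised during therapy.

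Two things are at stake. One is when study drug restarts after surgery. The other, if surgery falls in Course 1, is whether the patient can count towards the maximum tolerated dose (MTD). Section 9.1 bases its decisions on 6 patients and then on at least 12, so one patient's inclusion should not depend on which section the site read.

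**Working it through.** **Inputs.** Hold of at least 28 days after surgery (6.3.8). Hold on Days 13–16, restart on Day 17 (6.1.2). Course 1 schedule of one dose on Day 1, none on Day 2 and two a day on Days 3–28 (Table 4). Thresholds of 45/53 and 23/27 (12.1).

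**1. Reproduce the plan's denominators.**

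- Twice daily: 1 + 0 + 26 × 2 = 53 doses. Threshold 45/53 = 84.9%.
- Once daily (Dose Level 0, BSA 0.55–1.0 m²): 1 + 0 + 26 = 27 doses. Threshold 23/27 = 85.2%.

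Both agree with Section 12.1.

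**2. Restart day under Section 6.3.8.** Earliest restart = surgery day + 28. The example gives hold days but no surgery date, so each compatible date is shown.

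| Surgery day | Earliest restart (6.3.8) | Days after Day 17 |
|---|---|---|
| 12, after the last dose | 40 | 23 |
| 13 | 41 | 24 |
| 14 | 42 | 25 |
| 15 | 43 | 26 |
| 16 | 44 | 27 |

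A Day 17 restart that met Section 6.3.8 would need surgery on Day 17 − 28 = −11, before the course began. Dosing through Day 12, as in the example, would then itself breach the hold.

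**3. Course 1 dose count.**

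| | Twice daily | Once daily |
|---|---|---|
| Example (hold Days 13–16) | 53 − 8 = 45 (84.9%) | 27 − 4 = 23 (85.2%) |
| 6.3.8 (no dose from Day 13 to Day 28) | 53 − 32 = 21 (39.6%) | 27 − 16 = 11 (40.7%) |

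The second row is the same for surgery on any of Days 12–16, because the last dose is on Day 12 and every compliant restart is after Day 28. The first row sits exactly on the threshold, so one more missed dose would fail it. The second row is far below, and a patient without a DLT is replaced.

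**The case against.** The strongest reply is that the contradiction lies in a single parenthetical example. The general sentence in Section 6.1.2 is permissive and compatible with a specific surgical minimum. Sections 6 and 6.1.1 send questions and deviations to the study leadership, and Section 12.1 already replaces under-dosed patients. This limits the consequences, but it does not tell a site which instruction to follow. The allowance in Section 6 for minor unavoidable departures concerns clinical and scheduling problems, and it does not choose between two rules.

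A reader might infer more than the documents support:

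- **That a 28-day hold forces a dose reduction or removal.** Section 7.1.2 says a patient who is "delayed > 7 days from the planned start of the next course should be dose reduced", or goes off treatment if already at 80 mg/m². Days 40–44 are 11 to 15 days past Day 29. But 7.1.2 is headed as a toxicity rule, and Section 6.1.2 restarts non-toxicity holds at the same dose with course days continuing. On that counting Course 2 begins on schedule with drug on hold, and restart falls on its Day 12 to 16 (40 − 28 to 44 − 28), so its start is not delayed. Section 7.0 also requires the Study Chair or Co-Chair to be told before any dose modification.
- **That Section 6.1 is a third conflicting rule.** It permits restart at the physician's discretion after LMWH contraindications in general. That permission can coexist with a 28-day surgical minimum.
- **That the Day 17 patient is evaluable.** The count of 45/53 meets only the dose test. Section 12.1 also requires complete monitoring and no confounding supportive care.
- **That Day 17 is too early.** That presumes Section 6.3.8 governs. Section 3.1.6 suggests so but does not settle it.

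**Conclusion.** The inconsistency is real: the Section 6.1.2 example and the Section 6.3.8 hold cannot both be followed. Within the stated hold days they differ by 24 to 27 days. In Course 1, for a patient without a DLT, the choice decides whether the dose-count part of evaluability is met.

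This rests on three assumptions: surgery falls on Day 12 after the last dose or on Days 13–16; 28 days after surgery means the surgery day plus 28; and the evaluability denominator is the first 28 days, as Section 12.1 has it. The example refers to any course, so the evaluability consequence applies only when the surgery is in Course 1.

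The conflict concerns study drug only, because the two sections' LMWH instructions are compatible. The documents give neither the frequency of surgery nor data on harm from an earlier restart, so neither can be estimated and no safety effect is claimed. The sample size is not affected. The point should be corrected, but it does not threaten the design.

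**What to change.** Default, because Section 3.1.6 uses the same interval and exception: in Section 6.1.2, replace the shunt-revision example with a non-surgical hold, such as the bleeding-risk injury already listed in Section 6.1. Add a pointer to Section 6.3.8 for surgery in Section 6.1.2, and in Section 6.1 for planned invasive procedures.

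Alternative, if the sponsor intends a shorter hold for shunt revisions: keep the example, and add that exception with its restart condition to Section 6.3.8.

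Optional clarification: state in Section 6.3.8 that a surgical hold is a non-toxicity hold under Section 6.1.2, with the same dose and with course days continuing across the course boundary, so the 7-day delay rule in Section 7.1.2 does not apply.

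The cost is one example or one exception, two cross-references and, if wanted, a sentence or two in the next amendment, plus a short memo to sites. No new procedures are needed. Section 12.1 and the sample size stay as they are, since replacement is already provided for.

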### 6.4 Duration of Therapy

In the absence of treatment delays due to adverse event(s), treatment on study may continue up to 26 courses (approximately 2 years) or until further disease progression, unacceptable toxicity, withdrawal of consent, or until one of the following Off Treatment criteria in [Section 6.4.2](#) applies.

#### 6.4.1 On Study Data Submission Schedule

Pre-treatment, on-study, and off-treatment data, as well as patient response data are to be recorded in the electronic data collection screens using the RAVE database. See the Required Data and Timetable for Submission form located on the PBTC-056 Protocol Webpage for the schedule. For assistance, contact the PBTC Protocol Coordinator listed on the cover page.

#### 6.4.2 Off Treatment Criteria

At the discontinuation of treatment, the "Off Treatment Date" is to be recorded in the eCRF and is to be consistent with the reason given for going off treatment. The "Last Treatment Date" is defined as the last date that the patient received protocol based therapy. The reason for discontinuation of treatment must be documented by the attending investigator in the medical record and recorded in the eCRF.

Patients will be considered Off Treatment for the following reasons:

- Development of unacceptable toxicity as outlined in [Section 6.2](#). See [Section 10.3](#) and [10.4](#) for specific reporting requirements.
- Progressive disease (PD) as described in [Section 12.2](#).
- Development of a medical or psychiatric illness that in the investigator's judgment renders the patient incapable of further therapy on this protocol or the treating physician determines continuation on this study is not in the patient's best interest.
- The patient, parent, or legal guardian refuses further treatment on this protocol. In this case the investigator should clarify if the family also wishes to withdraw consent for continued participation for data collection purposes.
- Completion of all protocol defined treatment
- Pregnancy
- Non-Compliance that in the opinion of the investigator does not allow for ongoing participation.

- Termination of the study by the sponsor
- Investigational agent manufacturer can no longer provide the study agent.
- Development of a non-central line related thrombosis

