### 7.1 Hematologic and Non-hematologic Adverse Events and Management

#### 7.1.1 Dose Modification for Thromboembolic Toxicity

Thromboembolic event *	Management
Grade 1	Manage superficial thrombosis as per institutional standards, no change in dose needed.
Grade 2 **	Thromboembolic events should be managed as per institutional standards. Unless thrombosis is catheter-associated, discontinue INCB007839. If catheter-associated, hold INCB007839 until catheter-associated thrombosis is resolved.
Grade 3	Thromboembolic events should be managed as per institutional

Thromboembolic event *	Management
	standards. Discontinue INCB007839.
Grade 4	Thromboembolic events should be managed as per institutional standards. Discontinue INCB007839.
* Patients requiring a delay of > 14 days should go off protocol therapy.	
** Please note: Grade 2 superficial thrombophlebitis should be considered a Grade 1 thromboembolic event and managed as per the Grade 1 management above.	

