### 9.0 STATISTICAL CONSIDERATIONS

#### 9.1 Study Design/Endpoints

The primary aims of this study are to evaluate the safety and tolerability of INCB007839 and identify the maximum tolerated dose or the recommended phase 2 dose in children and young adults with recurrent/progressive CNS tumors. Based on this approach we propose to enroll 6 patients at Dose Level 1. If we observe no more than 1 DLT, enrollment on this dose level will be expanded to at least 12 subjects in order to obtain additional PK and safety information. If Dose Level 1 is not tolerable then we will de-escalate to Dose Level 0 and repeat the same process. If more than 3 DLTs are observed in 12 subjects at Dose Level 1, then the initially identified MTD based on 6 subjects will be considered unsafe and a dose de-escalation to Dose Level 0 will be considered.

We will use a design similar to the Rolling-6 design and open 6 slots initially on Dose Level 1. If we observe no-more than 1 DLT in these 6 subjects then we would expand this cohort to at least 12 patients for PK and additional safety information. If more than 1 DLT is observed on Dose Level 1 in 2–6 subjects, then further enrollment to Dose Level 1 will stop, the dose will be de-escalated to Dose Level 0 and the same approach will be repeated.

Based on the above-outlined de-escalation rules, if Dose Level 0 is found to be too toxic, then the trial will be closed to accrual and the merits of amending or closing the trial permanently will be reconsidered.

Accrual will be suspended for any Grade 5 AE which is at least possibly attributable to the study agent until a full assessment can be made. At that time, the toxicity data and all associated information will be reviewed by the study committee, the PBTC toxicity monitoring committee and DSMB, CTEP, and by the FDA prior to a deliberate decision to resume accrual.

Similarly, if a patient on this study has a thrombotic/thromboembolic event that is not related to the central line (except superficial phlebitis), treatment with INCB007839 will be discontinued and not restarted for that subject. Determination of attribution will be reviewed by the study team and discussed with PBTC Toxicity Committee and CTEP. A list of such events that will be reported to the CTEP-AERS, PBTC DSMB, and the FDA as events of special interest in an expedited fashion are in [Section 10.3](#).

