## 10.1 Comprehensive Adverse Events and Potential Risks List

### 10.1.1 Adverse Events List for INCB007839

#### **COMMON, SOME MAY BE SERIOUS**

In 100 people receiving INCB007839, more than 20 and up to 100 may have:

- Thrombotic events including pulmonary embolism, DVT, and superficial thrombophlebitis
- Nausea
- Vomiting
- Anorexia
- Flatulence
- Diarrhea
- Headache
- Dizziness
- Drowsiness
- Tinnitus
- Fatigue
- Fever
- Dehydration
- Pain
- Bleeding from the nose
- Dyspnea

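### The off-treatment list in 6.4.2 stops drug for low-grade superficial thrombosis that 7.1.1 keeps on treatment, and 9.1 and 6.2.1 do not carry the same exception

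*Combined protocol and SAP*

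**What the plan says.** Five places in the combined protocol and SAP bear on a clot that is not related to a central line.

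- **6.4.2 Off Treatment Criteria** lists "Development of a non-central line related thrombosis". The bullet has no grade limit and no superficial exception.
- **6.2.1 (non-hematologic DLT)** makes the following a DLT: "Any deep venous thrombotic event (superficial phlebitis is excluded unless Grade 3 or 4 as above". The sub-bullet beneath it reads "If a patient on this study has a thrombotic/thromboembolic event that is not related to the central line, treatment with INCB007839 will be discontinued" and does not repeat the exclusion. It also halts enrollment while the event is reviewed.
- **7.1.1 (thromboembolic dose modification), Grade 1 row:** "Manage superficial thrombosis as per institutional standards, no change in dose needed". Its footnote adds that "Grade 2 superficial thrombophlebitis should be considered a Grade 1 thromboembolic event and managed as per the Grade 1 management above". Otherwise the Grade 2 row stops drug unless the clot is catheter-associated, and the Grade 3 and Grade 4 rows stop drug.
- **9.1 Study Design/Endpoints** applies discontinuation to a "thrombotic/thromboembolic event that is not related to the central line (except superficial phlebitis), treatment with INCB007839 will be discontinued". The exception here has no grade limit.
- **6.2, general bullet:** a drug-related adverse event in the first course that ends therapy for good is dose limiting.

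**The concern.** A site looking up an off-treatment decision would naturally go to 6.4.2, and a site looking up dosing would go to 7.1.1. For a low-grade superficial event away from a line, the two give opposite instructions: stop for good, or continue at the same dose.

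Two things are at stake. First, a child with recurrent high-grade glioma, for whom Section 2.1.1 says no effective treatment exists at that stage, could permanently lose study drug over an event the dosing table says needs no change. Second, the dose-finding data could be affected. If the drug is stopped under 6.4.2 in Course 1 and the event is judged at least possibly related, the general bullet in 6.2 makes it a DLT. The specific thrombosis bullet in 6.2.1 excludes the same event at low grade. Under 9.1, more than one DLT in the first 2–6 patients closes a dose level, so a single event classified differently by two sites would matter.

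**Working it through.** No arithmetic applies, so the check sets the rules side by side for each kind of event.

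| Event, not line-related | 6.4.2 | 7.1.1 | 9.1 | Agree? |
|---|---|---|---|---|
| Grade 1 superficial thrombosis | Off treatment | Same dose | Exception names phlebitis only | No |
| Grade 1–2 superficial thrombophlebitis | Off treatment | Same dose | Excepted, if phlebitis includes it | No |
| Grade 2 superficial thrombosis that is not thrombophlebitis | Off treatment | Grade 2 row: discontinue | Not excepted | Yes |
| Grade 3–4 superficial phlebitis | Off treatment | Discontinue | Excepted (no grade limit) | No; 9.1 is the outlier |

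**Does the 6.4.2 bullet reach superficial events?** In this protocol's own usage, on balance, yes. Section 10.1.1 groups them together: "Thrombotic events including pulmonary embolism, DVT, and superficial thrombophlebitis". Section 2.2.2.2 counts a mild superficial thrombophlebitis among the nine adult thrombotic events. Section 7.1.1 grades superficial thrombosis on its thromboembolic scale. The exception was written into 9.1 and into the parent bullet of 6.2.1, which suggests the authors thought it was needed wherever the rule appears.

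**Is there a precedence rule?** Sections 6.0, 6.2, 6.2.2 and 6.2.3 send the reader to Section 7 or to the protocol's guidelines. The sentence in 6.2.2, for example, is "Management and dose modifications associated with the above adverse events are outlined in" Section 7. These pointers concern dose modification; none says Section 7 overrides an off-treatment criterion. Section 6.4 says treatment runs until one of the 6.4.2 criteria applies, so 6.4.2 is operative text.

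**The DLT chain, step by step.**
1. A superficial event away from a line occurs in Course 1 and is judged at least possibly drug-related.
2. Under 6.2.1's thrombosis bullet it is not a DLT at Grade 1 or 2.
3. Under 6.4.2 the patient goes off treatment permanently.
4. Under the general bullet in 6.2, a related event that causes permanent cessation is a DLT.

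Under 7.1.1 step 3 does not happen, and step 4 does not follow. The DLT status of the event therefore depends on which section the site applied.

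**A narrower neighbour.** Take a catheter-associated deep clot of Grade 2, at least possibly related, in Course 1 at Dose Level 0, resolving within 14 days. Section 7.1.1 holds drug until resolution. Section 6.2.1 makes the event a DLT, with no catheter exception in that line, and 6.2.4 discontinues a Dose Level 0 patient who has a DLT. The Grade 2 row does not mention this consequence.

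**The case against.** The strongest reply is that the intended rule is plain. The 6.2.1 parent bullet, 7.1.1 and 9.1 all spare low-grade superficial phlebitis or thrombophlebitis, several sections direct dose modification to Section 7, and the 6.4.2 bullet reads like a one-line summary. Section 7.0 also requires the Study Chair or Co-Chair to be notified before a dose modification, which may catch individual cases. Following 6.4.2 literally stops a drug with a suspected pro-coagulant effect, so the error is in the cautious direction for thrombosis. All of this stands and limits the seriousness. It does not remove the conflict, because an off-treatment criterion is an instruction and nothing ranks it below the table.

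A second reply concerns vocabulary. Section 10.3.4 keeps superficial thrombophlebitis and phlebitis out of its list of thromboembolic events for special expedited reporting, so the reach of the 6.4.2 bullet to phlebitis is arguable. That is fair. The conflict is clearest for the Grade 1 row, which uses the words superficial thrombosis.

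Three stronger readings are tempting and are not supported:

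- *That every Grade 1–2 superficial clot is meant to continue.* The 7.1.1 footnote downgrades only Grade 2 superficial thrombophlebitis. Other Grade 2 superficial thrombosis falls under the Grade 2 row, which stops drug unless the clot is catheter-associated. An exception for all Grade 1–2 superficial thrombosis would loosen that rule.
- *That the Dose Level 0 catheter case is an equal contradiction.* It needs several conditions at once. The specific rule in 6.2.4 largely settles it, and 7.0 allows no dose below Level 0. A related event that delays treatment by more than 7 days is a DLT under 6.2 in any case.
- *That the adult data give a usable frequency.* Section 2.2.2.2 reports one superficial thrombophlebitis among 41 adults, at 300 mg SR BID on warfarin, and does not say whether it was line-related. No rate for this trial follows from that.

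**Conclusion.** The inconsistency is real and lies in operative text. Section 6.4.2, and the 6.2.1 discontinuation sentence read on its own, stop drug for a Grade 1 superficial thrombosis or a Grade 1–2 superficial thrombophlebitis that is not line-related; 7.1.1 continues it at the same dose, and 9.1 exempts superficial phlebitis. Separately, the 9.1 exception is too wide, because it has no grade limit while 7.1.1 discontinues at Grade 3–4.

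The conflict holds for every such event, at either dose level and in any course. The DLT consequence is narrower: Course 1 only, and only when the event is at least possibly drug-related. The conclusion assumes that the word thrombosis in 6.4.2 carries the meaning it has in 2.2.2.2, 7.1.1 and 10.1.1.

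This is a wording correction worth making, because thrombosis was the declared adult dose-limiting toxicity and the stopping rule for it should read the same everywhere. A reader might infer that the plan deliberately stops children for trivial superficial events, or that its thrombosis safeguards are unsound. The documents support neither: other sections spare low-grade superficial phlebitis or thrombophlebitis, and the rules for deep and Grade 3–4 events away from a line are strict.

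**What to change.** 1. In the 6.4.2 thrombosis bullet and in the 6.2.1 discontinuation sentence, add: *except Grade 1 superficial thrombosis or Grade 1–2 superficial phlebitis/thrombophlebitis, managed per Section 7.1.1*.
2. Replace the open-ended exception in 9.1 with the same grade-limited wording.
3. As a minor addition, note in the catheter provision of the 7.1.1 Grade 2 row that a Dose Level 0 patient whose event is a DLT discontinues per 6.2.4.

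The exception is limited so that it tracks 7.1.1 as it stands and does not extend to Grade 2 superficial thrombosis other than thrombophlebitis. The cost is wording at four places (6.4.2, 6.2.1, 9.1 and 7.1.1). There are no added procedures or patients, and the dose-finding rules do not change.
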